#### 6.2.1.3.5 Adverse Events of Special Interest

Adverse events of special interest to Sponsor in this study include grade 4 local skin reactions seen under the patch while the patch is still applied on the skin or upon removal of the patch from the skin. Skin reactions will be examined at the time points specified in the Schedule of Procedures ([Table 7](#)) according to grading in [Table 6](#) ([Section 6.2.8](#)). Specifically, the appearance of any vesicles or ulcerative skin lesions or any other significant skin lesion which could potentially lead to skin barrier disruption at sites of Viaskin® patch applications will be considered AESI. Subjects (parents/guardians) will be instructed to take a photograph in case of appearance of any vesicles or ulcerative skin lesions. In these rare specific cases, subjects should transiently discontinue patch application and return to the site for evaluation and treatment of the wounded area, as well as for the next patch application and adequate evaluation and treatment of the wounded zone.

Upon re-application of the new patch, the subject should remain at the site for 1 hour before being discharged. The site must contact the subject (parents/guardians) by phone the day after this visit to ensure that no additional local blisters or vesicles developed and to confirm that the treatment can continue normally.

Any occurrence of IgE-mediated systemic-type of symptoms distant from the patch application site and considered at least possibly related to the study drug will also be considered as AESI and analyzed specifically as such at the end of the study at the time of the final analysis of study results.

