### **7.2.13 Unscheduled Visit**

Subjects may come to the site for visits outside of the scheduled visits in case of AEs, Viaskin® patch adhesion problems, etc.

The following assessments will be performed at these visits, at the discretion of the Investigator:

- Physical examination (including a complete skin examination; see [Section 6.2.4](#));
- Vital signs (see [Section 6.2.3](#));
- Spirometry (FEV1) (see [Section 6.2.5](#));

- PEF (see [Section 6.2.6](#));
- Laboratory tests ([Section 6.2.2](#));
- AEs recording (including volunteered or solicited AEs and AESI);
- Concomitant medications (see [Section 5.8](#));
- Check for any accidental peanut consumption (see [Section 6.4.4](#));
- Check subject diary;
- Dispense a new box of study drug (re-instruct subject/parents/guardians on the proper application, timing and storage, if necessary);
- Check unused medication and assess medication compliance;
- Patch adhesion Investigator's assessment: with the patch still applied, the Investigator assesses the adherence of the patch to the skin as well as the occlusion of the patch chamber;
- Check skin reactions under or around the current patch (do not remove patch) and all other zones of application and grade severity of the skin reactions (see [Table 6, Section 6.2.8](#));
- Take a photograph of the sites of application of the Viaskin® patch, load it onto the PEPITES website (described in [section 6.2.8](#)) and keep it in the subject's medical records or source documents.

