#### 8.2.2.3 *Unscheduled Assessments*

Extra assessments (laboratory data or vital signs associated with non-protocol clinical visits or obtained in the course of investigating or managing AEs) will be included in listings, but not summaries. If more than 1 laboratory value is available for a given visit, the first valid observation will be used in summaries and all observations will be presented in listings. It is noted that invalid laboratory data may not be used (from

hemolyzed samples, mishandled samples, quantity not sufficient, or other conditions that would render values invalid).

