### **8.6.7 Skin Reactions**

Viaskin® patch site examination data will be summarized where appropriate and listed. Examination of the skin at the site of patch application will be graded by the Investigators on a scale of Grade 0 (negative) to Grade 4 (erythema, vesicles). Localization of the skin reaction (under the patch/beyond the patch) will also be collected. These results will be summarized using descriptive statistics and presented by visit and treatment group, regardless of the localization as well as for each type of localization. The worst grade reported will also be tabulated. The above descriptions will be presented for the overall Safety population as well as for the age ranges 4 to 5 years, 6 to 8 years and 9 to 11 years and for each screening ED stratum.

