- Change from Baseline will be summarized using shift tables where appropriate.

The following conventions will be considered regarding study assessments and time points:

- Date and time of the first patch application will be reported in the eCRF. The baseline value is the last measurement before date and time of first patch application, in other words, Visit 4 data are taken into account for the Baseline, unless the date/time clearly indicates that the value is after the patch application. For physical exam, even if the time is not reported, V4 will be taken into account as Baseline.
- The ‘end of study’ assessment is defined as the last available post-treatment assessment.
- “Treatment Day” will be calculated relative to date of first patch application (Treatment day 1 = Date of first patch).
- Assessments collected at unscheduled visits will not be included in summary tables but only listed.
- Assessments outside of protocol allowable windows will be taken into account in the analysis according to the visit in which the data are entered.
- Early termination assessments will be analyzed as having occurred at the next scheduled assessment.

The following conventions will be considered regarding confidence p-values and confidence intervals (CI):

- P-values greater than or equal to 0.001, in general, will be presented to three decimal places. P-values less than 0.001 will be presented as “<0.001”.
- Confidence intervals will be presented to one more decimal place than the raw data.

The following conventions will be applied on diary data dates, for each incomplete patch application or removal date:

- Incomplete application date:
  - ⌘ During the first 14 days of patch application: imputed as removal dates (if removal date is complete).
  - ⌘ Beyond the first 14 days: imputed as removal date -1 (if removal date is complete).

- Incomplete removal date:
  - ⌘ During the first 14 days of patch application: imputed as application date (if application date is complete).
  - ⌘ Beyond the first 14 days: imputed as application date +1 (if application date is complete).

No imputations will be performed on time of application/removal unless explicitly described for specific analyses.

Titles for tables and listings produced will specify the type of data reported as well as the population concerned (in parentheses).

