#### 4.9.4 Local skin reactions as graded by the investigator at each visit

Local skin reactions at sites of Viaskin® application are graded by the investigator at each visit. More specifically at Visit 4, this evaluation is performed prior to the application and 30 minutes, 1 hour, 2 hours and 3 hours after the administration. These graded reactions will be reported in summary tables showing the number and percentage of subjects:

- By grade (by localization and regardless of the localization) by study visit
- By most severe grade (by localization and regardless of the localization) for the overall treatment period.

The above analysis will be repeated for subjects with filaggrin gene mutations versus wild type subjects.

All local skin reactions as graded by the investigator will also be listed.

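### SAP 4.2 keeps unscheduled-visit skin gradings out of the most-severe-grade table, which can therefore understate the worst grade reported

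*SAP*

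**What the plan says.** - SAP 4.2 (General Considerations): "Assessments collected at unscheduled visits will not be included in summary tables but only listed". A separate item in the same list keeps Early Termination assessments, which are analysed at the next scheduled assessment.
- SAP 4.9.4 plans two summaries of the investigator's skin grades: one by visit, and one "By most severe grade (by localization and regardless of the localization) for the overall treatment period". It states no exception to the rule in 4.2. It adds that "All local skin reactions as graded by the investigator will also be listed".
- Protocol 8.6.7, on the same data: "The worst grade reported will also be tabulated". It does not restrict this to scheduled visits.
- Protocol 8.2.2.3 has its own listing-only rule. It opens "Extra assessments (laboratory data or vital signs associated with non-protocol clinical visits" and names no other kind of assessment.
- Protocol 6.2.1.3.5, on vesicles, ulcerative lesions and other significant lesions at patch sites: "subjects should transiently discontinue patch application and return to the site for evaluation and treatment of the wounded area".
- Protocol 7.2.13: "Subjects may come to the site for visits outside of the scheduled visits in case of AEs". Checking and grading the skin is on the list of assessments for these visits, at the investigator's discretion.
- SAP 4.13, which lists changes from the protocol, does not mention the treatment of unscheduled assessments.

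**The concern.** A maximum over the treatment period is only as complete as the gradings that feed it. The rule in SAP 4.2 removes the visits that take place because something went wrong. A child who returns with vesicles (grade 4 in protocol Table 6) and is graded only at that visit would appear in the most-severe-grade table at the highest grade seen at a routine visit.

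Dropping observations can lower a maximum but never raise it, so any error runs towards milder grades. It would fall mainly on the active arm: in the Phase IIb study, protocol 1.1.1.2.3 reports a higher percentage of subjects with skin reactions of higher severity in each active group than on placebo, at all time points. Investigator-assessed local severity is a named safety criterion (protocol 3.2.2, SAP 3.2), and grade 4 local reactions are adverse events of special interest. Grades below 4 can also be affected, because protocol 5.2 and 7.2.5 allow a child to be seen earlier than planned after a safety phone contact.

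**Working it through.** **Text check.** The documents give no figure to reproduce, so the first step is to follow the rules in order.

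1. Vesicles or ulceration at a patch site lead to a return to the site (protocol 6.2.1.3.5). The return is driven by the event, so it will often fall between scheduled visits.
2. A visit outside the schedule for an adverse event is an unscheduled visit, at which the skin can be graded (protocol 7.2.13).
3. Under SAP 4.2 that grade is listed and not summarised. SAP 4.9.4 does not override this.
4. The grade is therefore missing from the most-severe-grade table, although protocol 8.6.7 asks for the worst grade reported and protocol 8.2.2.3 does not name skin gradings among the data kept to listings.

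**How many children might have a grade 4 reaction.** Protocol Table 3 (Phase IIb study, children aged 6 to 11) classes application site vesicles as uncommon: at least 1/1,000 and under 1/100. For the 220 children planned on active treatment:

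- lower end: 220 × 1/1,000 = 0.22
- upper end: 220 × 1/100 = 2.2

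**Share of lesions that scheduled visits would miss.** The documents give no lesion duration, so I assume 7, 14 or 21 days. Nominal grading days after Day 1 are taken as 8, 30, 91, 182, 274, 365 and 370 (Day 8, Months 1, 3, 6, 9 and 12, and Visit 11), ignoring visit windows. A lesion that starts on day s and lasts d days is seen at a visit on day v if v − d + 1 ≤ s ≤ v. Count the start days covered by at least one visit:

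| Duration d | Covered, onset Days 1-365 | Missed | Covered, onset Days 1-60 | Missed |
|---|---|---|---|---|
| 7 days | 6 × 7 = 42; 42/365 = 11.5% | 88% | 7 + 7 = 14; 14/60 = 23% | 77% |
| 14 days | 8 + 5 × 14 = 78; 78/365 = 21.4% | 79% | 8 + 14 = 22; 22/60 = 37% | 63% |
| 21 days | 8 + 5 × 21 = 113; 113/365 = 31.0% | 69% | 8 + 21 = 29; 29/60 = 48% | 52% |

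The Day 8 visit covers at most 8 start days. Visit 11 adds none, because its start days up to 365 are already covered by Month 12.

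The Days 1-60 columns reflect protocol 1.1.1.2.6, which says that most local skin reactions developed within the first 2 months. Protocol Table 4 shows a wider spread for all related TEAEs in children (37.03% before Day 90, 70.26% before Day 180), so the two onset patterns serve as reasonable bounds.

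**Combined.** Grade 4 cases not seen at any scheduled visit: from 0.22 × 0.52 = 0.11 to 2.2 × 0.88 = 1.9 children. This is a ceiling for the table's shortfall at grade 4, since some of these children may have no grading at the unscheduled visit either.

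**The case against.** The strongest reply is that these events are reported elsewhere. All adverse events from the first dose go into the e-CRF (protocol 6.2.1.4). SAP 3.1 keeps only itching, redness and swelling at the patch site off the adverse event form, with stated exceptions; vesicles and ulcers are not among them. They therefore reach the TEAE, related-TEAE and local-TEAE tables (SAP 4.9.1), none of which depends on visit type. This stands. A reader might infer that grade 4 reactions disappear from the safety reporting, and the documents do not support that. The AESI table is a weaker safeguard: SAP 4.9.5 finds local cases by the text GRADE 4 or GRADE IV in the verbatim term, so a report of vesicles alone could be missed there. Neither route corrects the most-severe-grade table.

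A reader might also infer larger numbers from two other rates in the protocol. Neither fits this trial. The 2.0% grade 4 rate in CoFAR6 for ages 6 and over (220 × 2.0% = 4.4) comes from one adolescent, and the group aged 4 to under 6 had 0.0%. The single case among 221 Phase IIb subjects has a denominator that includes placebo, lower doses, adolescents and adults.

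Three further limits stand. Grading at unscheduled visits is discretionary. Protocol 6.2.8 grades all previous patch sites together, which may lengthen the time a lesion remains gradable and so reduce the share missed. Early Termination data are already retained.

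Finally, the heading of SAP 4.9.4 refers to each visit, and its second summary covers the whole treatment period, so a programmer might include unscheduled gradings. The explicit general rule in 4.2 points the other way, and no exception is written. That conflict is itself a reason to add a sentence.

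**Conclusion.** The point holds for one descriptive table. Followed as written, SAP 4.2 removes from the most-severe-grade table any grade recorded only at an unscheduled visit. The table can then fall short of what protocol 8.6.7 promises, and SAP 4.13 does not disclose the departure from protocol 8.2.2.3.

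The size is small in number of children. For grade 4, about 0.2 to 2.2 of 220 active children would be expected to have such a reaction, and scheduled visits would miss roughly half to nine-tenths of these lesions (52-77% with early onset, 69-88% with uniform onset). Those shares rest on assumed durations of 7 to 21 days and nominal visit days, and are illustrations rather than estimates. The frequency class comes from children aged 6 to 11 and is not broken down by dose. With so few cases, losing one or two could empty the grade 4 row. The effect on lower grades cannot be quantified from the documents. No efficacy result or success criterion is touched.

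**What to change.** 1. In SAP 4.9.4, state that the most severe grade over the treatment period uses all investigator gradings, scheduled and unscheduled. By-visit tables stay with scheduled visits. Early Termination needs no new wording because SAP 4.2 already includes it.
2. Either align the unscheduled-visit rule in SAP 4.2 with protocol 8.2.2.3, or list the broader rule in SAP 4.13 as a change from the protocol.

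The cost is one sentence, one consistency edit and one change to a derived variable. No new data are needed, since unscheduled gradings are already due to be listed. The downside for the sponsor is that the active arm's worst-grade distribution may look slightly less favourable.

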### 4.3 Study Subjects

#### 4.3.1 Disposition of Subjects

A clear accounting of the disposition of all subjects who enter the study will be provided, from screening to study completion.

Subject disposition will be summarized for all subjects, overall and by screening ED subgroup.

Reason for non-randomization will be listed for screened subjects who failed to be randomized.

The number of screened subjects will be provided.

The number and percentage of randomized subjects, who completed the study and those who discontinued the study together with the primary reason for discontinuation from the study will be tabulated overall and by treatment group.

All the above percentages will be expressed based on the number of subjects in the ITT population.

The number and percentage of subjects randomized in total, by region (Australia / Europe / North America), by country and by site will be summarized overall and for each treatment group.

Additionally, an enrollment summary will be presented overall, by site, country and region showing the number of subjects screened, randomized and completing the study and among randomized subjects: the first date of consent, the last study visit date, the study duration (in days - calculated as last study visit exit date – first date of consent for first screened subject +1).

Study disposition and termination details will be listed for each subject. Listings will also be created to show the study analysis set classifications and randomization assignments.

#### 4.3.2 Protocol Deviations

Deviations from the protocol including violations of inclusion/exclusion criteria will be assessed as “minor” or “major” in cooperation with the Sponsor prior to unblinding.

Major protocol deviations (PDV) are defined as those deviations from the protocol likely to have an impact on the perceived efficacy and/or safety of the study treatment. The impact of major PDV on the efficacy and/or safety results will be investigated by assessing the robustness of the study results and conclusions to the choice of analysis population (see [Section 4.4](#)), both including and excluding data potentially affected by major PDV.

Observable PDV data will be entered into PAREXEL’S Clinical Trials Management System (CTMS). Some PDV will be identified via programmed edit checks and listings. The study team and the Sponsor will conduct on-going reviews of the PDV data from the CTMS and the PDV listings and the resulting set of evaluable subjects throughout the study, adjusting the PDV criteria (major/minor PDV) as appropriate.

The evaluable subject sets must be finalized prior to database lock.

PDV will help to define the subjects to be excluded from the PP population.

The two following violation criteria (as Mentioned in [Appendix 1: Major Protocol deviations](#)) have been pre-defined to be excluded subjects from the PP analysis:

- Subjects who do not perform the DBPCFC at 12 months of EPIT treatment,
- Subjects with global treatment compliance below 80%.

Listings will be created to aid the review of data and identification of possible PDV.

The number and percentage of subjects with major PDV will be summarized by type of deviation, overall and by treatment group for all randomized subjects. All PDV data will be listed.

Major PDV and any action to be taken regarding the exclusion of subjects or affected data from specific analyses are specified in [Appendix 1: Major Protocol deviations](#).

#### 4.4 Analysis Populations

After database lock, analysis population outputs will be produced and will be sent to DBV Technologies for review. These outputs will first be blindly reviewed and discussed during the Blinded Data Review meeting and it will be decided which subjects and/or subject data will be excluded from certain analyses. Decisions made regarding the exclusion of subjects and/or subject data from analyses will be made prior to blind breaking and will be documented and approved by DBV Technologies in the Blinded Data Review minutes.

A summary of the number and percentage of subjects included in each analysis population described below (Intention to treat population [ITT], Safety set, Full analysis set [FAS], Per-protocol population [PP]) will be provided overall and by treatment group.

A by-subject listing of analysis populations (based on screened subjects) will be provided ordered by treatment group and will include: treatment group, subject identifier, and inclusion/exclusion flag for each population and reason for exclusion from each population.

The populations described in the following paragraphs will be considered.

##### 4.4.1 Screened Population

The screened population consists of subjects whose parents/guardians have signed informed consent.

##### 4.4.2 Intent-to-treat Population

The ITT population will be comprised of all subjects who are randomized. This population will be used to assess comparative efficacy information. Subjects will be analyzed according to the treatment they have been randomized to.

##### 4.4.3 Full analysis set

The FAS will be comprised of all ITT subjects who are randomized and have performed at least the peanut challenge of the second DBPCFC at Month 12 (M12). Subjects will be analyzed according to the treatment they have been randomized to.

##### 4.4.4 Per-protocol Population

A PP population will be used to perform sensitivity analyses of the primary and secondary evaluations. This PP population will include all subjects from the ITT population who do not have major deviations from the protocol that may affect the primary (and secondary) efficacy endpoints. The deviations to consider will be listed more in detail in [Appendix 1: Major Protocol deviations](#) of this SAP and will be reviewed

CCI

CONFIDENTIAL

Project Document Version No. 3.0

Project Document Effective Date: 04-Oct-2017

Page 24 of 79

during the Blinded Data Review Meeting. This population will be analyzed according to study treatment that was actually received by the subjects. In case the wrong study drug is taken, the subject will be analyzed according to the study drug received for the longest period of time. In the event that a subject is stratified incorrectly (i.e. the screening ED recorded in the IWRS differs from the actual one), actual screening ED value (Screening ED subgroup) will be used rather than ‘randomized stratum’.

#### 4.4.5 Safety Population

The safety population will be comprised of all subjects who are randomized and have received at least one dose of study drug. This population will be used to assess comparative safety information. In case the wrong study drug is dispensed, the subject will be analyzed according to the study drug received for the longest period of time. In the event that a subject is stratified incorrectly, ‘actual’ screening ED value will be used rather than ‘randomized stratum’.

A subject is assumed to have received at least one dose of study drug:

- If the date/time of first dose is completed in the eCRF
- Or if at least one patch adhesion scoring is completed (in case the date of first dose is missing)

#### 4.5 Demographics and Baseline characteristics (including medical history, parental atopic history and disease history)

Demographic, Baseline characteristics (including medical history, parental atopic history and disease history) will be summarized by treatment group and overall for the Safety population (globally and by screening ED subgroup) as well as for the ITT population and for the FAS. If the Safety population is identical to the ITT population, tables will not be duplicated and ITT population will be used.

Balance between treatment groups at Baseline on the Safety population (globally and by screening ED subgroup) will be assessed using statistical tests on a selection of key variables, identified in the below sections.

Statistical tests used will be:

- a Student’s t-test for continuous variables anticipated to have a normal distribution
- a Mann-Whitney test for continuous variables anticipated to have a non-normal distribution
- a  $\chi^2$  test for categorical variables (Fisher’s exact test if one or more theoretical frequency is  $\leq 5$ ).

All subject demographic characteristics and Baseline characteristics will be listed.

